11.2 Clinical Laboratory Tests

Clinical laboratory tests will be performed to assess eligibility for enrolment and will be repeated according to the schedule of assessment. Laboratory tests can be repeated more frequently, if clinically indicated.

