 - Increases in ECOG PS ≥ 3 that resolves to ≤ 2 by Day 1 of the next infusion (ie, infusions should not be given if the ECOG PS is ≥ 3 on the day of treatment and should be delayed until ECOG PS ≤ 2).
 - Keratoacanthomas and/or cSCC (see Section 6.8.3 for management).
- See Appendix 1 for suspected Grade 3 irAEs as many require permanent treatment discontinuation, including pneumonitis and nephritis.
 - AST or ALT > 5 times ULN or total bilirubin greater than 3 times ULN must be permanently discontinued, except for participants with liver metastases (for example) who begin treatment with Grade 2 AST or ALT. These participants should be discontinued if AST or ALT increases by $\geq 50\%$ relative to baseline and lasts for at least 1 week.
- Persistent Grade 3 adverse reactions (excluding endocrinopathies controlled with hormone replacement therapy) that do not recover to Grade 0 to 1 within 12 weeks after dose of treatment.

Grade 2 ADRs should be managed as follows:

- a. If a Grade 2 ADR resolves to Grade ≤ 1 by the day before the next infusion, treatment may continue.
- b. If a Grade 2 ADR does not resolve to Grade ≤ 1 by the day before the next infusion, but it is manageable and/or not clinically relevant, the PI should be consulted to assess if clinically reasonable to administer the following infusion.

16 Discontinuation of Study Intervention and Participant Discontinuation/Withdrawal

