21 STUDY ASSESSMENTS AND PROCEDURES

Baseline evaluation:

Investigations	Timing		
History and Physical Exam including:	Treatment history Medical history Smoking history Height and weight	Vital signs ECOG PS TNM stage	Within 14 days prior to treatment initiation
Current Smoking Status and Tobacco Use	Assessment of patient's current smoking status and tobacco use		Within 14 days prior to treatment initiation
Symptoms & Toxicities	Evaluation and documentation of symptoms and toxicities using the NCI CTCAE v5.0		Within 14 days prior to treatment initiation
Concomitant Medications	Documentation of concomitant medications		Within 14 days prior to treatment initiation
Hematology and Coagulation	CBC with hemoglobin, platelets, and WBC with differential Prothrombin time (PT) / Partial thromboplastin time (PTT)		Within 14 days prior to treatment initiation
Biochemistry	Albumin Alkaline phosphatase Potassium Total bilirubin, direct, indirect BUN Creatinine Total protein Free T4, TSH	Glucose LDH SGOT (AST) SGPT (ALT) Sodium Magnesium Uric acid	Within 14 days prior to treatment initiation

Pregnancy Test	Urine or serum (for women of childbearing potential only)	Within 48 hours prior to treatment initiation
Radiology	CT chest	Within 30 days prior to treatment initiation
Radiology	PET-CT	Within 60 days prior to treatment initiation
Radiology	MRI brain or CT brain (only for patients with stage II or III on pre-operative staging)	Within 60 days prior to treatment initiation
Mediastinal staging	CT chest / PET-CT, mediastinoscopy, and/or endobronchial ultrasound	Within 60 days prior to treatment initiation
Pulmonary tests	Complete pulmonary function test	Within 60 days prior to treatment initiation
Tumor/Adjacent Lung Tissue Collection for Biomarkers	Archival tissue or new biopsy of primary tumor for biomarker analysis (optional) Tissue obtained for mediastinal staging (optional)	Prior to treatment initiation
Blood-based biomarkers	Blood sample	Prior to treatment initiation
Stool-based Microbiome	Stool sample	Prior to treatment initiation
Pharmacokinetic (PK) studies	Blood sample	Prior to infusion and immediately after infusion of dose #1 of M7824
Anti-Drug Antibodies (ADA) studies	Blood sample	Prior to infusion of dose #1 of M7824

Evaluation during neoadjuvant treatment (prior to each M7824 infusion):

Investigations		Timing	
Physical Exam Including:	BSA Vital signs	Within 7 days prior to dose #2 and #3 of M7824	

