Hematology	CBC with hemoglobin, platelets, and WBC with differential	Within 7 days prior to dose #2 and #3 of M7824	
Pregnancy Test	Urine or serum (for women of childbearing potential only)	Within 7 days prior to dose #2 and #3 of M7824	
Biochemistry ¹	Albumin Alkaline phosphatase Total bilirubin, direct, indirect BUN Creatinine Total protein Free T4, TSH	Glucose LDH Potassium SGOT (AST) SGPT (ALT) Sodium Magnesium Uric acid	Within 7 days prior to dose #2 and #3 of M7824
Radiology ¹	CT chest PET-CT	At least 14 days after the last dose of M7824	
Symptoms & Toxicities	Evaluation and documentation of symptoms and toxicities using the NCI CTCAE v5.0	On an ongoing basis throughout the study until the final study visit	
Concomitant Medications	Documentation of concomitant medications	On an ongoing basis throughout the study until the final study visit	
Blood-based biomarkers ¹	Blood sample	Within 7 days prior to dose #2 and #3 of M7824 and at least 14 days after the last dose of M7824	

Pharmakokinetic (PK) studies	Blood sample	Prior to infusion of dose # 2 Prior to infusion and immediately after infusion of dose #3 At least 14 days after the last dose of M7824
Anti-Drug Antibodies (ADA) studies	Blood sample	Prior to infusion of dose #3 of M7824 At least 14 days after the last dose of M7824
Pulmonary tests	Complete pulmonary function test ²	At least 14 days after the last dose of M7824
Stool-based Microbiome	Stool sample	At least 14 days after the last dose of M7824
¹ If information / studies have already been obtained but therapy is delayed for any reason, repeated studies are not necessary prior to next cycle of therapy. ² Complete pulmonary function test may not be required if patient is no longer considered a surgical candidate post neoadjuvant therapy based on the treating physician's discretion.		

Assessments at surgery:

Investigations	Timing
Surgical procedure	Title of operation Status of resection margins (R0, R1, R2)
Tumor Tissue Collection	ypTNM Major pathologic response Percentage of viable tumor cells Nodal stations dissected / sampled and nodal status (positive vs. negative) at each station Evaluation of extra-capsular nodal spread

End of treatment assessments:

Investigations		Timing
Physical Exam Including:	Vital Signs	Approximately within 8 weeks after surgery
Blood-based biomarkers	Blood sample	Approximately within 8 weeks after surgery

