
Monitor patient for abnormal liver blood tests: AST, ALT, and bilirubin prior to each infusion and/or weekly if G1 liver function test elevations. No treatment is recommended for G1 liver function test abnormality
 
For G2 or higher:
 
Work-up for other causes of elevated liver enzymes should be tested, viral hepatitis, alcohol history, iron study, thromboembolic event, liver ultrasound, cross-sectional imaging for potential liver metastasis from primary malignancy. If suspicion for primary autoimmune hepatitis is high, can consider ANAs, antismooth muscle antibodies, antineutrophil cytoplasmic antibodies. If patients with elevated alkaline phosphatase alone, g-glutamyl transferase should be tested. For isolated elevation of transaminases, consider checking CK for other etiologies
	
Grading	Management
All patients	
Counsel all patients to be aware of and inform their health care provider immediately if they experience:
 
Yellowing of skin or whites of the eyes Severe nausea or vomiting Pain on the right side of the abdomen Drowsiness Dark urine (tea colored) Bleeding or bruising more easily than normal Feeling less hungry than usual

G1: Asymptomatic (AST or ALT > ULN to 3.0 x ULN and/or total bilirubin > ULN to 1.5 x ULN)	
Continue ICPi with close monitoring; consider alternate etiologies Monitor laboratories one to two times weekly Manage with supportive care for symptom control

G2: Asymptomatic (AST or ALT > 3.0 to \leq 5 x ULN and/or total bilirubin > 1.5 to \leq 3 x ULN)	
Hold ICPi temporarily and resume if recover to G1 or less on prednisone \leq 10 mg/d For Grade 2 hepatic toxicity with symptoms, may administer corticosteroid 0.5-1 mg/kg/d prednisone or equivalent if the abnormal elevation persists with significant clinical symptoms in 3-5 days Increase frequency of monitoring to every 3 days Infliximab might not be the most appropriate treatment option in the situation of immune- mediated hepatitis given the potential risk of idiosyncratic liver failure (Note: No clear evidence shows the liver toxicity from infliximab from other studies) In follow-up, may resume ICPi treatment followed by taper only when symptoms improve to G1 or less and corticosteroid \leq 10 mg/d; taper over at least 1 month

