
Definition: T2DM is a combination of insulin resistance and insufficiency that may require oral or insulin therapy. It may be new onset or exacerbated during therapy for nonimmunologic reasons, such as corticosteroid exposure.
 
Autoimmune T1DM results from islet cell destruction and is often acute onset, with ketosis and an insulin requirement
 
Diagnostic work-up
 
Monitor patients for hyperglycemia or other signs and symptoms of new or worsening DM, including measuring glucose at baseline and with each treatment cycle during induction for 12 weeks, then every 3-6 weeks thereafter. To guide the work-up in new-onset hyperglycemia, clinicians should consider a patient's medical background, exposure history, and risk factors for each subtype of DM.
 
Laboratory evaluation in suspected T1DM should include testing for ketosis in urine and an assessment of the anion gap on a metabolic panel. Anti-glutamic acid decarboxylase, anti-islet cell, or anti-insulin antibodies are highly specific for autoimmune diabetes. Insulin and C-peptide levels can also assist in the diagnosis.
									

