5.0 Musculoskeletal Toxicities	
	Should initiate prednisone 20 mg/d or equivalent. If no improvement or need for higher dosages for prolonged time, may offer a corticosteroid-sparing agent such as methotrexate or IL-6 inhibition with tocilizumab (Note: As caution, IL-6 inhibition can cause intestinal perforation; while this is extremely rare, it should not be used in patients with colitis or GI metastases). Consider admission for pain control
All recommendations are expert consensus based, with benefits outweighing harms, and strength of recommendations are moderate.	

Abbreviations: ADL, activities of daily living; ALT, alanine aminotransferase; ANA, antinuclear antibodies; AST, aspartate aminotransferase; CCP, citrullinated protein antibody; CK, creatine kinase; CRP, C-reactive protein; DMARD, disease-modifying antirheumatic drug; EMG, electromyography; ESR, erythrocyte sedimentation rate; G, Grade; HLA, human leukocyte antigen; ICPI, immune checkpoint inhibitor; IL, interleukin; irAE, immune-related adverse event; IV, intravenous; IVIG, intravenous immunoglobulin; LDH, lactate dehydrogenase; MRI, magnetic resonance imaging, NSAID, nonsteroidal anti-inflammatory drug; PCP, Pneumocystis pneumonia; RF, rheumatoid factor; TB, tuberculosis; TNF, tumor necrosis factor.

Table A6

Management of Renal irAEs in Patients Treated With ICPis

<h3 style="text-align: center;">6.0 Renal Toxicities</h3>	

Nephritis and renal dysfunction: diagnosis and monitoring For any suspected immune-mediated adverse reactions, exclude other causes Monitor patients for elevated serum creatinine prior to every dose Routine urinalysis is not necessary, other than to rule out UTIs, etc; nephrology may consider further If no potential alternative cause of AKI identified, then one should forego biopsy and proceed directly with immunosuppressive therapy Swift treatment of autoimmune component important
	
<h4>6.1 Nephritis</h4>	

Definition: Inflammation of the kidney affecting the structure
	
Grading	Management
G1: Creatinine level increase of > 0.3 mg/dL; creatinine 1.5-2.0 x over baseline	Consider temporarily holding ICPi, pending consideration of potential alternative etiologies (recent IV contrast, medications, fluid status) and baseline renal function. A change that is still < 1.5 ULN could be meaningful

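### Footnote 1 of the on-treatment schedule lets a delayed dose 2 or 3 be given on biochemistry older than the row's own 7-day window, with no maximum result age

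*Combined protocol and SAP*

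**What the plan says.** The on-treatment table in Section 21 gives one timing to four rows (physical exam, hematology, pregnancy test and biochemistry): "Within 7 days prior to dose #2 and #3 of M7824". Of these four, only Biochemistry carries footnote 1. Radiology and Blood-based biomarkers also carry it. Under the footnote, where studies are already in hand and "therapy is delayed for any reason, repeated studies are not necessary prior to next cycle of therapy". No upper limit on result age is given.

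The biochemistry row contains AST, ALT, bilirubin, creatinine and glucose, among others. Several dosing rules depend on them:

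- Section 15.3, on Grade 3 reactions, says that patients with "AST or ALT > 5 times ULN or total bilirubin greater than 3 times ULN must be permanently discontinued" (the exception is for patients who start with raised values, for example from liver metastases).
- Appendix 1, Table A2 defines Grade 2 hepatitis as asymptomatic, with AST or ALT above 3 and up to 5 times ULN and/or bilirubin above 1.5 and up to 3 times ULN. The instruction is "Hold ICPi temporarily and resume if recover to G1 or less on prednisone" at a low dose.

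On monitoring, Table A2 asks for "AST, ALT, and bilirubin prior to each infusion and/or weekly if G1 liver function test elevations". Table A6 says "Monitor patients for elevated serum creatinine prior to every dose". Table A4 asks for "measuring glucose at baseline and with each treatment cycle during induction for 12 weeks". None of these states how recent the sample must be. Section 11.2 adds: "Laboratory tests can be repeated more frequently, if clinically indicated".

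**The concern.** A 7-day window exists so that the result describes the patient about to be dosed. The footnote removes that assurance for chemistry whenever a dose is late, whatever the cause and however long the delay, yet keeps it for the CBC and the physical exam. The protocol gives no reason for treating the two kinds of blood test differently.

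The patient at issue had a normal panel before the planned dose and was then delayed for something unrelated to the liver or kidney. The protocol itself makes such delays foreseeable. Section 15.2 recommends a 2-week delay from treatment after minor surgery, Section 5.1 asks for biopsy of suspicious skin lesions, and Table A1 suggests considering a hold for Grade 2 rash. Section 13 also contemplates non-medical gaps.

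A transaminase or creatinine rise during such a delay may cause no symptoms, and exam, CBC and symptom review would not show it. Section 3.7 lists increased transaminase and acute renal injury among the drug's important identified risks. What is at stake is re-dosing a patient whom the protocol's own rules would have held or stopped.

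**Working it through.** The plan states no figure to reproduce. The check is a reading of the table followed by day arithmetic.

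**Which rows are waived**

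| Row | Window before doses 2 and 3 | Footnote 1 |
|---|---|---|
| Physical exam | 7 days | no |
| Hematology (CBC) | 7 days | no |
| Pregnancy test | 7 days | no |
| Biochemistry | 7 days | yes |

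Radiology (at least 14 days after the last dose) and Blood-based biomarkers are also marked, but the hold and stop rules quoted above do not rest on them.

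**Is chemistry age capped elsewhere?** Section 11.2, Section 15.3 and Appendix 1 contain no cap. A sample drawn before the delay is still a sample drawn before the infusion, so it satisfies the wording of Tables A2 and A6.

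**Result age at a delayed dose**

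Inputs:
- Doses on days 1, 15 and 29 (Section 9.1).
- Tolerance of 3 days either way (synopsis).
- Panel drawn 0 to 7 days before the planned date (Section 21).
- Insufficient-adherence criterion when, after one missed cycle, the interval exceeds 4 weeks for non-medical reasons (Section 13).
- Permanent discontinuation indicated if a Grade 2 or 3 reaction has not recovered within 12 weeks of the last dose (Section 15.3).

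If the dose is given d days after its planned date, result age = d to d + 7 days.

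- *d up to 3.* This is inside the dosing tolerance, so therapy is not clearly delayed and the footnote is not clearly triggered. These cases are left out.
- *d = 4, the first day beyond tolerance.* Age 4 to 11 days. Panels drawn more than 7 − 4 = 3 days before the planned date are already out of window.
- *d above 7.* The youngest possible result is older than 7 days, so every pre-delay panel is out of window.
- *Non-medical delay to the 4-week mark.* Dose 1 on day 1, dose 2 on day 1 + 28 = 29, so d = 29 − 15 = 14. Age 14 to 21 days, which is two to three times the window.
- *Prolonged toxicity hold to the 12-week mark.* Dose 2 on day 1 + 84 = 85, so d = 85 − 15 = 70. Age 70 to 77 days.

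The same arithmetic applies to dose 3, with the clock starting at dose 2. In every case beyond d = 7, the CBC and exam would have to be repeated and the chemistry would not.

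**Exposure.** Doses 2 and 3 in 23 patients make at most 2 × 23 = 46 doses. The documents do not say what fraction would be delayed, or how often AST, ALT or creatinine rises without symptoms.

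**The case against.** The strongest reply is that the waiver is permissive and that other text already points clinicians to fresh tests. Section 11.2 allows extra testing, and Appendix 1 ties liver tests, creatinine and glucose to each infusion, dose or cycle. Many toxicity holds would generate chemistry anyway. Recovery from hepatitis or nephritis can be shown only by repeat values. Grade 2 colitis calls for a comprehensive metabolic panel, severe cutaneous reactions for liver and kidney tests, and myositis lists transaminases. The plan also accepts chemistry up to 14 days old before dose 1.

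Much of this stands, and it confines the gap to delays for other reasons. It does not close the gap. A repeat under Section 11.2 needs a clinical indication, and a well patient with a normal earlier panel offers none. The work-ups for other toxicities are done at diagnosis and are not required again at re-dosing. For rash, liver and kidney tests are done only if needed. A non-medical delay triggers none of them. Before dose 1 the patient has had no study drug, so the longer baseline window is not a precedent.

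A reader might infer that the footnote contradicts Appendix 1. It does not, because the appendix sets no age limit. A reader might also infer that patients held for hepatic or renal toxicity can be re-dosed without new values. The hold-and-resume rules for those toxicities do not support that.

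**Conclusion.** The gap is real and minor. Followed as written, the schedule allows dose 2 or 3 to be given on chemistry outside its own 7-day window after a delay of more than 3 days unrelated to hepatic or renal toxicity. In that situation the Table A2 hold and the Section 15.3 stop could be missed for a silent rise. A fair illustration is chemistry 14 to 21 days old at a 4-week interval.

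Two stronger readings should be resisted.

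- *That results 70 to 77 days old are to be expected.* That is an outer bound. It requires a toxicity hold lasting to the 12-week limit, and Section 9.2 allows surgery after fewer than three doses. Section 13 makes a non-medical gap beyond 4 weeks a matter of insufficient adherence, which may lead to discontinuation; it is a soft limit, not an automatic stop.
- *That a number of missed cases can be estimated from the 377 pooled subjects in Section 3.7.* Those data list treatment-related immune events by term where two or more subjects were affected. They do not give the rate of asymptomatic AST, ALT or creatinine rises, and there is no delay rate to combine with it.

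The conclusion rests on the footnote marks as they appear in the table. If Hematology were also meant to be marked, the gap would be wider. No endpoint, sample size or monitoring boundary is affected.

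**What to change.** At the next amendment, remove superscript 1 from the Biochemistry row, so that the panel must fall within 7 days before the date on which dose 2 or 3 is actually given, as for Hematology. Leave the footnote on Radiology and Blood-based biomarkers.

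The cost is one deleted superscript and one extra chemistry panel for each delayed dose whose earlier result has gone out of window. It can be drawn at the same time as the CBC that the schedule already requires.

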22 STATISTICAL CONSIDERATIONS

This is an open label phase II study with a modular design. Currently, eligible patients will be accrued to the M7824 monotherapy arm (Arm A). The primary objective is to evaluate the rate of MPR, rather than hypothesis testing with pre-specified null and alternative MPR rates. There will be no interim futility nor efficacy monitoring. The primary efficacy endpoint of the study is MPR evaluated in resected tumor tissues following neoadjuvant therapy and defined as $\leq 10\%$ viable tumor cells in the resected specimen using the methods described by Pataer et al. (2).

Analysis of primary efficacy endpoint:

A sample size of 23 patients is proposed for each arm of the study. With an estimated accrual rate of 2-3 patients a month, the accrual period is approximately 15-24 months. We will estimate the MPR rate with a 95% credible interval (CI) assuming that the MPR rate follows a prior beta distribution (0.5, 0.5) with one patient worth of information. For example, if the M7824 monotherapy indeed has a true MPR rate of 30% and 7 patients with MPR are observed in this study, the corresponding 95% CI of the observed MPR rate would be (14.8%, 50.7%).

Furthermore, we calculated predictive probability of $\text{Prob}(p > 0.15 | \text{data and true MPR rate})$ for a variety of true MPR rates, where p is the MPR rate. As shown in the table below (**Table 3**), there will be a fairly high chance (81 – 89%) for the study to observe a MPR rate $> 15\%$ with a sample size of 23 patients if the true MPR rates are 25% and higher.

Table 3. Predictive probabilities of true MPR rates.

True MPR rate	predictive probability of $\text{Prob}(p > 0.15 \text{data and true MPR rate})$ where $a_0=0.5, b_0=0.5$
---------------	--

0.05	12%
0.10	30%
0.15	50%
0.20	67%
0.25	81%
0.30	89%

We chose to use 15% MPR rate as cutoff because a historic major pathologic responserate to neoadjuvant chemotherapy alone of 19% is observed (as described by Pataer et al.) (2). However, some patients that receive neoadjuvant chemotherapy may not receive surgery for one reason or another, and these cases will be considered treatment failure. Assuming the 19% major pathologic response rate is calculated from 80% of patients who receive surgery, a conservative estimate of the major pathologic response is 15%.

Analysis of Secondary/Exploratory Endpoints:

Analysis for the secondary/exploratory endpoints will be descriptive and exploratory in nature. Descriptive statistics will be provided to summarize the data distribution. Association analysis by Pearson or Spearman correlation coefficient will be calculated for continuous data and chi-square or Fisher's exact test for categorical data. Time-to-event endpoints will be computed using the Kaplan-Meier method. Multivariate analysis will be used to explore the role of biomarkers in predicting pathologic response to treatment, in an exploratory way. The goals forthese analyses are for hypothesis generating. The results will need to be confirmed by future studies.

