5. HYPOTHESIS

The primary research question to be tested in this study is whether in patients with stage I-IIIA NSCLC amenable for surgical resection, induction immunotherapy with 3 doses of M7824 monotherapy will produce major pathologic responses in resected tumors as determined by Pataer et al. (JTO 2012).

The secondary research question to be tested in this study is that immunotherapy with M7824 will induce immune responses (as assessed by CD8+ TILs), tumor shrinkage (as assessed by CT), and improve recurrence-free survival (RFS) and overall survival (OS) in a subset of patients; analysis of correlative studies in these patients will assist in developing biomarkers predictive of response to immunotherapeutic agents in NSCLC and will assist in determining immune modulation by M7824.

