6. STUDY ENDPOINTS

6.1 Primary Endpoints

- Major pathologic response (MPR) rate in patients treated with induction M7824 monotherapy.

MPR is defined as $\leq 10\%$ viable tumor cells in the resected specimen using the methods described by Pataer et al (20). Briefly, at least 1 section per cm of tumor greatest diameter is evaluated, with a minimum of 5 slides. The percentage of residual tumor is determined by comparing the estimated cross sectional area of the viable tumor foci to estimated cross sectional areas of necrosis, fibrosis and inflammation on each slide. The results for all slides are averaged together to determine a mean value of viable tumor cells for each patient.

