8.2 Study Plan

This is an open label, phase 2 platform study with modular design testing the experimental agent M7824 in the neoadjuvant setting. We will start investigating M7824 monotherapy induction treatment in patients with resectable NSCLC, with the primary objective to determine the MPR in each arm, and compare it not between arms, but to the benchmark from historical controls of neoadjuvant chemotherapy.

After confirmation of eligibility criteria, patients will be enrolled in Arm A. Sequential arms investigating induction M7824-based strategies may be added after completion of enrollment in Arm A.

Arm A — M7824 monotherapy

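### The 15% benchmark counts unresected patients as failures, but the plan does not say whether unresected M7824 patients count in the MPR denominator

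*Combined protocol and SAP*

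**What the plan says.** **The benchmark.** Section 22 starts from the statement that "a historic major pathologic responserate to neoadjuvant chemotherapy alone of 19% is observed". It then notes that "some patients that receive neoadjuvant chemotherapy may not receive surgery for one reason or another, and these cases will be considered treatment failure", continues "Assuming the 19% major pathologic response rate is calculated from 80% of patients who receive surgery", and concludes that "a conservative estimate of the major pathologic response is 15"%. The synopsis repeats this reasoning. Section 8.2 gives the benchmark its role: the plan is to determine MPR in each arm and "compare it not between arms, but to the benchmark from historical controls of neoadjuvant chemotherapy".

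**The M7824 endpoint.** The cues differ by place.

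- Section 22: "The primary efficacy endpoint of the study is MPR evaluated in resected tumor tissues following neoadjuvant therapy".
- Section 5 asks whether three doses "will produce major pathologic responses in resected tumors".
- Section 6.1: "Major pathologic response (MPR) rate in patients treated with induction M7824 monotherapy". The synopsis likewise refers to patients treated with induction M7824.
- Section 22's worked interval and Table 3 are both for 23 patients, the full planned enrolment of Arm A.

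**Patients without surgery.** The plan expects that some may occur. A footnote to the on-treatment assessments in Section 21 covers patients who are no longer surgical candidates after induction. Section 23 lists severe pneumonitis that prevents the planned resection as an unacceptable toxicity. Neither place, nor any other, says how such a patient enters the MPR rate.

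**The concern.** A rate and its benchmark have to share a denominator. The benchmark was lowered from 19% to 15% precisely because chemotherapy patients who miss surgery are charged as failures. If M7824 patients who miss surgery through progression, toxicity or refusal are simply left out, the new drug is not charged for the same event. They have no specimen, so they never contribute a response; leaving them out only shrinks the denominator. The resulting error runs in one direction, towards M7824.

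There is no formal test, so this is not a type I error problem. The rate still has consequences. Section 8.2 compares it with historical chemotherapy, and Section 8.1 lets the next step (a randomised comparison or a different single-arm study) depend on whether a signal of activity is seen. In an open-label single-arm trial, a denominator left open can also be chosen after the results are known.

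**Working it through.** **Inputs.** From Section 22: historical MPR 19%, assumed chemotherapy resection rate 80%, cutoff 15%, n = 23, Beta(0.5, 0.5) prior. My assumption for the no-gain scenario: M7824 equals chemotherapy, with 19% MPR among resected patients and 80% resected.

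**1. The plan's own figures.**

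- Benchmark: 0.19 × 0.80 = 0.152, stated as 15%.
- Interval for 7 responses: with n = 23 the posterior is Beta(7.5, 16.5), whose 2.5% and 97.5% points are 14.8% and 50.7%, as printed. With n = 18 it would be Beta(7.5, 11.5), giving 19.4% to 61.7%. The example therefore uses all 23.
- Table 3: the mean posterior probability, Σₓ Bin(x; 23, p) × P(rate > 0.15 | Beta(0.5 + x, 23.5 − x)), gives 12.0, 30.2, 50.0, 67.4, 80.5 and 89.3% for p = 0.05 to 0.30. The plan prints 12, 30, 50, 67, 81 and 89%. Again n = 23.

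**2. No-gain scenario, same metric as Table 3.** Expected number resected: 23 × 0.80 = 18.4, taken as 18.

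| M7824 rate | Set against | Mean posterior probability of exceeding the cutoff |
|---|---|---|
| Resected only (n = 18, p = 0.19) | 15% | 62.6% |
| All treated (n = 23, p = 0.19 × 0.80 = 0.152) | 15% | 50.8% |
| Resected only (n = 18, p = 0.19) | 19% | 50.0% |
| All treated (n = 23, p = 0.152) | 19% | 36.5% |

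The two matched rows sit near 50%, as they should when there is no gain. The mismatch in the first row adds 62.6 − 50.8 = 11.8 points. Letting the number resected vary binomially instead of fixing it at 18 gives 62.8%. The last row is the opposite mismatch, which works against M7824.

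**3. Dependence on the M7824 resection rate** (assumed values, 19% MPR if resected, cutoff 15%):

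| Resection rate | Resected only | All treated | Difference |
|---|---|---|---|
| 100% | 64.2% | 64.2% | 0 |
| 90% (21 of 23) | 63.6% | 57.7% | 5.9 points |
| 80% (18 of 23) | 62.6% | 50.8% | 11.8 points |
| 70% (16 of 23) | 61.9% | 43.4% | 18.5 points |

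The resected-only figure hardly moves as more patients miss surgery, whereas the all-treated figure falls.

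**4. Same data, two denominators.**

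| Responses | Observed, n = 23 | P(rate > 0.15) | Observed, n = 18 | P(rate > 0.15) |
|---|---|---|---|---|
| 3 | 13.0% | 0.42 | 16.7% | 0.61 |
| 4 | 17.4% | 0.65 | 22.2% | 0.81 |
| 5 | 21.7% | 0.82 | 27.8% | 0.93 |

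With three responses, the denominator alone moves the observed rate across 15%.

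**5. The 80%.** It is labelled an assumption and the documents give no source. Taking 70% to 100% as a range gives benchmarks of 0.19 × 0.70 = 13.3% to 0.19 × 1.00 = 19%.

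**The case against.** The best defence is that the plan already means all treated patients. Section 6.1 is where the endpoint is defined, and it speaks of patients treated; the synopsis agrees; the interval and Table 3 only work with 23. The Section 22 and Section 5 wording can fairly be read as saying where MPR is measured, since it can be measured nowhere else. The failure sentence is in the future tense and sits in the paragraph that justifies this trial's cutoff, so it may have been meant to cover M7824 as well. On that reading 15.2% is like for like and nothing is biased.

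Much of this stands. A reader might infer from Section 22 that the endpoint is written for resected tumours only and that the comparison is therefore biased as planned. The documents do not support that, for the reasons just given. But the defence does not close the gap. The failure sentence is about chemotherapy patients, and planning calculations at n = 23 do not say what happens to a patient without a specimen. The resected-only habit is also present in the protocol: Section 3.12 reports neoadjuvant nivolumab as 9 of 20 resected tumours.

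A second tempting reading is that calling 15% conservative shows the bar was set leniently. In context the word describes a low estimate of the chemotherapy rate. As a hurdle, 15% is easier to clear than 19%, but for an all-treated rate it is the matched figure, not a lenient one. This is a point of wording.

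One could also quote the chance that the observed rate exceeds 15%, which in the no-gain scenario is 64% for resected-only and 47% for all-treated. That measure is not a decision rule in the plan and jumps with n (73% for 19 resected, 54% for 20), so I rely on the Table 3 metric.

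**Conclusion.** The plan has an undefined primary denominator with conflicting cues, set beside a benchmark that is clearly all-treated. The bias is conditional: it arises only if the M7824 rate is computed among resected patients and held against 15%. In that case, with no true gain and 80% resected, the mean posterior probability of exceeding the benchmark is about 63% rather than 51%. The gap is nil if every patient is resected and widens as fewer are. These sizes rest on the plan's own 19% and 80% carried over to M7824. The effect is on how a signal is read, not on an error rate. This should be corrected before the primary analysis, but it does not undermine the design or the sample size.

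**What to change.** In Sections 6.1 and 22, and in the synopsis:

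- State that the primary MPR rate uses all patients who received at least one dose of M7824, with those lacking resection counted as non-MPR.
- State that only this rate is compared with 15%. If a resected-only rate is also reported, compare it with 19%. Do not set the all-treated rate against 19%, which would create the reverse mismatch.
- Describe 15% as the like-for-like all-treated benchmark under an assumed 80% resection rate, give the 13.3% to 19% range for 70% to 100%, and drop the word *conservative*.

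The worked interval and Table 3 can stay, since they already use 23. No change to sample size, data collection or patient care is needed. The cost is a few sentences, and the headline rate may be slightly lower than a resected-only figure would be.
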